## Study Protocol

In this study, the combination of Pericapsular Nerve Group (PENG) block and low-dose intrathecal morphine with spinal anesthesia in hip arthroplasty is aimed to be compared with PENG alone and intrathecal morphine alone in terms of morphine consumption, postoperative pain, and recovery quality scores during the postoperative 48-hour period.

After approval from the Ethics Committee of Bezmialem Vakif University Medical Faculty, the study will be conducted on 90 adult patients aged 18-90 years, classified as ASA I-IV, who will undergo hip surgery. This prospective, randomized, and double-blind clinical trial has been planned. Randomization will be achieved by assigning patients to study groups entirely by chance, and selection bias will be prevented. For this purpose, MedCalc version 16 statistical software for Windows ([medcalc.com.tr](http://medcalc.com.tr)) will be used. Patients will be divided into three groups: Pericapsular nerve group block plus spinal anesthesia with bupivacaine (Group P: n=30), Spinal anesthesia with bupivacaine and morphine (Group M: n=30), and pericapsular nerve group block plus spinal anesthesia with bupivacaine and morphine (Group P+M: n=30). After the patients are taken to the operating room, standard monitoring with non-invasive blood pressure (NIBP), heart rate (HR), peripheral oxygen saturation (SpO2), and electrocardiography (EKG) will be conducted. All patients will receive 2-6 L/min of oxygen through a nasal cannula. Preoperative visual analog scale (VAS) for pain and Quality of Recovery (QoR-15) values will be recorded for all patients. As premedication, all patients will receive 0.03 mg/kg midazolam.

In this prospective, double-blind, randomized clinical trial, researchers will be unaware of which treatment will be applied to patients in the study groups and which of these treatments is beneficial or not. Patients will also be unaware of which treatment is administered to them.

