During the postoperative period, all patients will receive 1 g of intravenous paracetamol every 8 hours. Morphine PCA (concentration: 0.1mg/ml, bolus dose: 1 mg, lockout time: 10 minutes, basal infusion rate: 0 mg) will be adjusted, and intravenous Patient-Controlled Analgesia (PCA) will be applied.

Rescue analgesia will be provided with 50 mg tramadol upon request or when  $VAS \geq 4$  and will be recorded.

Patients experiencing nausea or vomiting at any time will receive ondansetron intravenously at a dose of 0.15 mg/kg, and this dose will be repeated if necessary.

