### Statistical Analysis

Descriptive statistics for qualitative variables in the study are presented as counts and percentages, while descriptive statistics for quantitative variables include mean, standard deviation, median, minimum, and maximum values. For comparisons based on the occurrence rates of relevant variables among groups, Pearson chi-square or Fisher Freeman Halton tests will be employed. In the detailed comparison of groups with observed differences, the Bonferroni correction will be applied. The normal distribution conformity of quantitative variables will be assessed using the Kolmogorov-Smirnov test. One-way analysis of variance (ANOVA) will be utilized for the comparison of means among more than two groups, with the Tukey test employed as a post hoc test for multiple comparisons. Kruskall-Wallis test will be applied for the median comparison of more than two independent groups, and Dunn test will be used for pairwise comparisons. For repeated measurements of variables showing normal distribution changes between periods, analysis of variance will be applied, while the Friedman test will be used for variables not showing normal distribution. Additionally, two-way analysis of variance will be used to

examine changes between groups and periods. The statistical significance level will be set at 0.05, and the SPSS (version 26) package program will be used for calculations. Consent to conduct the study was obtained from Local Ethic Committee of Bezmialem Vakif University.

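### Regular preoperative opioid use is not excluded, recorded or adjusted for, although PCA morphine consumption is the first-named outcome; the cost is precision, not bias

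*Combined protocol and SAP*

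**What the plan says.** The Study Protocol section describes the population in one sentence: "the study will be conducted on 90 adult patients aged 18-90 years, classified as ASA I-IV, who will undergo hip surgery". There is no list of exclusions, and preoperative opioid use is not mentioned anywhere.

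The three treatments are to be compared "in terms of morphine consumption, postoperative pain, and recovery quality scores during the postoperative 48-hour period". Morphine consumption comes first, but none of the three outcomes is named primary.

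Allocation is described thus: "Randomization will be achieved by assigning patients to study groups entirely by chance, and selection bias will be prevented". Three arms of 30 are planned and no stratification factor is given. The baseline versions of the outcome measures are collected ("Preoperative visual analog scale (VAS) for pain and Quality of Recovery (QoR-15) values will be recorded for all patients"), but no measure of prior opioid use is.

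The Groups section sets the patient-controlled pump at "bolus dose: 1 mg, lockout time: 10 minutes, basal infusion rate: 0 mg". It also says "Rescue analgesia will be provided with 50 mg tramadol upon request", with a pain-score trigger as well.

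The Statistical Analysis section names one-way ANOVA with Tukey, Kruskal-Wallis with Dunn, and a Kolmogorov-Smirnov normality check. It has no covariate and no sensitivity analysis for prior opioid use.

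**The concern.** Morphine taken from a patient-controlled pump reflects the patient's habitual opioid need as well as the block or the intrathecal morphine. With a 1 mg bolus every 10 minutes, the pump allows 6 mg/h, or 6 x 48 = 288 mg over the study period, so it would do little to cap a high consumer.

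A few such patients widen the spread of consumption within an arm. With 30 per arm and no stratification, they may also fall unevenly. If 10% of entrants are regular users, the chance that two given arms differ by three or more of them is about 27% (13% at 5%, 42% at 20%). What is at stake is the ability to detect a real difference in the first-named outcome. If prior use is not captured before allocation, it is hard to recover cleanly afterwards.

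**Working it through.** **Inputs from the documents.** 30 patients per arm; significance level 0.05, taken as two-sided because the plan does not say. The plan states no SD, effect size or power, so there is no sample-size figure to reproduce.

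**Assumed inputs.** Opioid-naive mean consumption 20 mg in one arm and 12 mg in the other; gamma-distributed with CV 0.6 (SDs 12 and 7.2 mg). A share p of entrants are regular users who consume m times as much, with the SD scaled likewise. The central case is p = 10%, m = 3.

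**Step 1: mixture moments, central case.**
- Means: 20 x (0.9 + 0.1 x 3) = 24 mg and 12 x 1.2 = 14.4 mg; difference 9.6 mg (8 mg with no regular users).
- Variance, higher arm: 0.9 x 12² + 0.1 x 36² + 0.9 x 0.1 x 40² = 403.2, SD 20.1 mg.
- Variance, lower arm: 0.9 x 7.2² + 0.1 x 21.6² + 0.9 x 0.1 x 24² = 145.2, SD 12.0 mg.

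**Step 2: rough power by normal approximation**, Φ(difference/SE - 1.96).
- No regular users: SE = √((144 + 51.84)/30) = 2.56; 8/2.56 = 3.13; power about 88%.
- Central case: SE = √((403.2 + 145.2)/30) = 4.28; 9.6/4.28 = 2.25; power about 61%.

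**Step 3: simulation** (8,000 two-arm comparisons per setting), which allows for the skewness.

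| Regular users | Means (Welch) | Ranks (Mann-Whitney) |
|---|---|---|
| none | 89% | 84-85% |
| 5%, twice the use | 84-85% | about 83% |
| 10%, three times | 66% | 77% |
| 15%, three times | 60% | not needed for the range |

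The two-arm tests stand in for the pairwise comparisons. Welch is not itself in the plan; Mann-Whitney is the two-group counterpart of Kruskal-Wallis.

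**Step 4: equivalent sample size.** In the same model, the 66% for means is what about 17-18 opioid-naive patients per arm would give. The 77% for ranks matches about 25 (25 per arm gives 78%).

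**Step 5: sensitivity to the model.** A three-arm simulation assumed instead an additive effect of 7.3 mg in one arm, naive mean 20 mg and SD 10 mg. At 10% and three times the use, ANOVA power fell from 0.84 to 0.36 and Kruskal-Wallis power from 0.83 to 0.63. Using the normality check to choose the test gave 0.62 with the Lilliefors version and 0.52 with the uncorrected Kolmogorov-Smirnov test. The uncorrected check sent only 48% of those trials to ranks. The loss is therefore larger if the treatment effect does not scale with consumption.

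**Step 6: type I error.** With no treatment effect and 10% regular users at three times the use, rejection rates were 0.046 (ANOVA) and 0.055 (Kruskal-Wallis), close to the nominal 0.05.

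**Step 7: effect of adjusting.** Back in the gamma model, adding a yes/no indicator of regular use as a covariate at 10% and three times the use raised power for the means from 66% to about 82-83%, with nobody excluded.

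**The case against.** The strongest reply is that the plan already holds a partial remedy. A sample with a few extreme consumers is likely to fail the normality check and go to Kruskal-Wallis/Dunn, where the central-case loss is about 8 points and the mild-case loss about 2. This stands in part: the rank route softens the loss, but it does not remove it, and the check as named does not reliably select it.

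Second, the eligibility of opioid users is inferred from silence, and a broad population is a defensible pragmatic choice. That also stands. No sentence sets out to enrol them, and their share among entrants is unknown. It does not explain why prior use goes unrecorded.

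Three stronger readings are tempting but not supported:
- *The comparison is biased or invalid.* Allocation is random and type I error stays near 5%. Uneven splits by chance are part of the sampling variation that the test already covers.
- *Thirty patients carry the information of about 11.* That comes from 30 x 144/403 = 10.7, which puts the higher arm's inflated variance in both arms and holds the difference at 8 mg. In this scenario the difference grows to 9.6 mg and the lower arm varies less. Eleven opioid-naive patients per arm would give only 43% power, not 66%.
- *The trial's outcome is opioid consumption, and a few patients will hide the effect.* Consumption is one of three outcomes with none named primary, and the rank analysis limits the influence of extreme values.

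**Conclusion.** The concern holds as a matter of precision. Nothing in the entry conditions, allocation, baseline data or analysis deals with prior opioid use, although the first-named outcome is directly sensitive to it. In the central case the loss is about 23 points of power for means (89% to 66%) and about 8 for ranks. In the mild case it is about 4 to 5 points and 2 points, and it is greater under an additive effect. All of these figures depend on assumed means, spread, prevalence and multiplier, so how much it matters at this hospital cannot be judged from the text. The change is worth making because it is cheap and has to be made before enrolment; it is not a flaw that invalidates the trial.

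**What to change.** Preferred: record regular preoperative opioid use, as a daily dose, for every patient before allocation, and prespecify it as a covariate in the comparison of morphine consumption. Kruskal-Wallis and Dunn take no covariate, so the Statistical Analysis section should say which adjusted model is the main analysis for this outcome and keep the rank test as a supporting one. The recovery to about 82-83% was simulated with a yes/no indicator; adjustment by dose was not simulated.

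Alternative: exclude regular preoperative opioid users, with a stated look-back period. Under the assumptions above this restores the full 89%.

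Cost: one case-report field and one covariate for the first route. The second needs one entry criterion, at the price of a slightly smaller and less general eligible population.

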### Groups:

**Group P:** Patients in this group will undergo ultrasound-guided block using a linear or convex ultrasound probe in the supine position before spinal anesthesia. The block procedure will involve the use of a local anesthetic solution (10-20 ml of 0.25% bupivacaine, 2 mg dexamethasone, and 5 mcg.ml-1 epinephrine) and a Stimuplex Ultra 360 22G 80 mm block needle (B. Braun Medical AG, Melsungen, Germany). Subsequently, spinal anesthesia will be administered at the L3-L4 intervertebral level with 10-15 mg of heavy bupivacaine while the patient is in a sitting position.

**Group M:** Patients will receive subarachnoid block without Pericapsular Nerve Group block. Subarachnoid block will be administered at the L3-L4 intervertebral level by adding 10-15 mg bupivacaine with 100 µg of morphine.

**Group P+M:** Patients will undergo ultrasound-guided block using a linear or convex ultrasound probe in the supine position before spinal anesthesia. The block procedure will involve the use of a local anesthetic solution (10-20 ml of 0.25% bupivacaine, 2 mg dexamethasone, and 5 mcg.ml-1 epinephrine)

and a Stimuplex Ultra 360 22G 80 mm block needle (B. Braun Medical AG, Melsungen, Germany). Subarachnoid block will be administered at the L3-L4 intervertebral level by adding 10-15 mg bupivacaine with 100 µg of morphine.

Sensory block control at T8-T10 level will be assessed in all three groups. Visual analog scale (VAS) for pain and 15-degree leg elevation will be measured in all groups 10 minutes after the completion of the block. Postoperative nausea and vomiting will be monitored and recorded. The same anesthesiologist will administer both the block and spinal anesthesia to all patients.

After the block, all patients will be continuously monitored for signs of local anesthetic toxicity every 5 minutes with non-invasive blood pressure, continuous EKG, and pulse oximetry, for 30 minutes. During the perioperative period, VAS (at 1st, 6th, 12th, 24th, and 48th hours), QoR-15 score values, and rescue analgesic requirements of patients will be recorded.

Intravenous Patient-Controlled Analgesia (IV PCA) device will be installed, and patients who are hemodynamically and respiratory stable in the recovery unit will be transferred to the ward.

During the postoperative period, all patients will receive 1 g of intravenous paracetamol every 8 hours. Morphine PCA (concentration: 0.1mg/ml, bolus dose: 1 mg, lockout time: 10 minutes, basal infusion rate: 0 mg) will be adjusted, and intravenous Patient-Controlled Analgesia (PCA) will be applied.

Rescue analgesia will be provided with 50 mg tramadol upon request or when  $VAS \geq 4$  and will be recorded.

Patients experiencing nausea or vomiting at any time will receive ondansetron intravenously at a dose of 0.15 mg/kg, and this dose will be repeated if necessary.

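### One operator who knows whether a PENG block was given chooses the spinal bupivacaine dose within an open 10-15 mg range, so dose can differ between Group M and the PENG arms

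*Combined protocol and SAP*

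**What the plan says.** All of the dosing text is under Groups.

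- **Spinal dose.** For Group P, "spinal anesthesia will be administered at the L3-L4 intervertebral level with 10-15 mg of heavy bupivacaine". For Groups M and P+M, "Subarachnoid block will be administered at the L3-L4 intervertebral level by adding 10-15 mg bupivacaine" together with 100 µg of morphine. No fixed dose and no height, weight or age rule is given.
- **Operator.** "The same anesthesiologist will administer both the block and spinal anesthesia to all patients".
- **Order and sham.** Patients in Groups P and P+M have an "ultrasound-guided block using a linear or convex ultrasound probe in the supine position before spinal anesthesia". For Group M, "Patients will receive subarachnoid block without Pericapsular Nerve Group block", and no sham is described.
- **Block volume.** Groups P and P+M receive "10-20 ml of 0.25% bupivacaine", again with no selection rule.
- **Level check.** "Sensory block control at T8-T10 level will be assessed in all three groups". Nothing links this check to the dose.

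The Study Protocol section says that researchers and patients will not know the treatment, but it describes no arrangement that would make this true of the operator. It gives no time at which allocation is opened. Nothing says that delivered doses will be recorded, compared or adjusted for.

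**The concern.** The trial compares the combination with each component alone, so the arms should differ only in PENG and intrathecal morphine. Spinal bupivacaine is common to all arms and should not depend on allocation. Here it is chosen after the operator has, or has not, just placed a PENG block. Randomization balances patient characteristics, but it does not protect a dose chosen once allocation is known.

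Suppose the operator compensates by giving more spinal bupivacaine when there was no block, and suppose a larger dose improves the outcome. Group M then looks better than it should. P+M versus M is diluted and P versus M is tilted toward M. The main harm would be lost power to show the benefit of the combination. Under a true null, the extra rejections would favor M. This direction is an assumption, because the documents give none.

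Block volume is a narrower matter. It can differ only between P and P+M, and only if the operator also knows morphine status, which the documents neither state nor exclude.

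**Working it through.** **The plan's own figure.** The plan gives 90 patients, 30 per arm, with no effect size, SD or power. There is no calculation to reproduce, so what follows is for scale only.

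**Inputs from the documents.** Three arms of 30; significance level 0.05; ANOVA with Tukey's test as the post hoc test on the normal-theory branch; spinal range 15 − 10 = 5 mg, so the top dose is 50% above the bottom.

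**Assumptions, not from the documents.**
- The outcome shifts by 0.1-0.5 SD across the full 5 mg.
- Mean dose differs between Group M and a PENG arm by 10%-50% of the range, i.e. 0.5-2.5 mg.
- For the power column, the true P+M versus M gap is the one that Tukey's test detects with 80% power.

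**Bias.** Bias = (shift across the range) × (fraction of the range). The lowest value is 0.1 × 0.1 = 0.01 SD and the highest is 0.5 × 0.5 = 0.25 SD.

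**Test constants.** Error df = 90 − 3 = 87. Tukey q = 3.372, so critical |t| = 3.372/√2 = 2.384. The SE of a pairwise difference is √(2/30) = 0.258 SD. A gap of 0.835 SD gives 80% power.

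**Rejection probabilities.** These come from the noncentral t distribution with df = 87 and noncentrality (true difference)/0.258. The null column uses the bias alone. The power column uses 0.835 minus the bias. For bias 0.25, for example, the noncentralities are 0.25/0.258 = 0.97 and (0.835 − 0.25)/0.258 = 2.27.

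| Bias (SD) | Per-pair null rejection | Power, P+M vs M |
|---|---|---|
| 0 | 1.93% | 80% |
| 0.01 | 1.94% | 79% |
| 0.05 | 2.15% | 74% |
| 0.10 | 2.83% | 68% |
| 0.15 | 4.03% | 61% |
| 0.25 | 8.32% | 46% |

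A simulation of 200,000 trials with only Group M shifted, by 0.25 SD, gave null rejection of 8.3% for P vs M, 8.3% for M vs P+M and 2.0% for P vs P+M. The last pair is unaffected by the spinal route as long as morphine status is masked.

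**Effect of committing the dose first.** Assume intended doses are uniform on 10-15 mg and that allocation-aware dosing raises each Group M dose by s mg, capped at 15 mg. The expected mean difference from the PENG arms is s − s²/10:

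- s = 1: 0.90 mg
- s = 2: 1.60 mg
- s = 2.5: 1.88 mg

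If the dose is written before allocation is opened and always followed, the expected difference is zero. Chance imbalance remains, with SE (5/√12) × √(1/30 + 1/60) = 1.443 × 0.224 = 0.32 mg. If it is followed in 90% of Group M patients, one tenth of the systematic difference remains, 0.09-0.19 mg. That 90% is also an assumption.

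**The case against.** The strongest objection is that the size is assumed. The documents connect neither spinal dose with 48-hour outcomes nor allocation with dose, and the slope could be zero. The worst row of the table needs both assumptions at their maximum. At the midpoints (0.3 × 0.3 = 0.09 SD) null rejection is 2.7% and power 69%, and up to 0.15 SD the null rejection rate stays below 5%. This stands: the table shows what could happen and does not demonstrate harm.

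The direction is assumed too. Less bupivacaine in Group M would reverse the tilt, and dosing by patient characteristics alone would remove it. This also stands.

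Tukey's test applies only if the ANOVA branch is used; the Statistical Analysis section otherwise sends outcomes to Kruskal-Wallis and Dunn. That changes the illustration but not the route by which bias could enter.

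A range is clinically reasonable for patients aged 18-90 and ASA I-IV, and a single operator removes differences between operators. Both are fair, and both are compatible with the fix, which keeps the range and the operator. A single operator does, however, put knowledge of the block and freedom over dose in the same hands.

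The general statement that researchers are unaware of treatment cannot hold for the person who places, or does not place, the block.

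**Conclusion.** The concern holds. The text supports every element of the route: an open range with no selection rule, one operator, the block before the spinal, and no sham in Group M. Spinal dose can therefore differ systematically between M and the PENG arms, and with no plan to report delivered doses a reader could not rule it out.

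Under the stated assumptions the consequence runs from negligible (0.01 SD) to a fall in power from 80% to 46% (0.25 SD). Confidence is medium, because slope, dose difference and direction are all assumed. It is worth acting on because the remedy is cheap and cannot be applied once the doses have been given.

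**What to change.** Keep both ranges. The plan already has a suitable moment, before any procedure, when preoperative VAS and "Quality of Recovery (QoR-15) values will be recorded for all patients". At that point, for each patient, the operator writes the intended spinal dose and the block volume to be used if a block is assigned. The protocol should state that allocation is opened only after this entry; without that, the entry gives no protection. The written amounts are then given unless there is a clinical reason to depart. The amount given and any reason are recorded, and delivered amounts are reported by arm. A fixed spinal dose, or a rule based on height or age, would serve the same purpose.

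The cost is one line on the case record and one or two protocol sentences, with no extra staff. The operator loses some freedom to adjust after allocation is known, but recorded clinical departures remain allowed, such as a volume change judged during the ultrasound-guided injection. This greatly reduces allocation-dependent dosing without eliminating it, and it does not cure the missing sham.

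### Nausea and vomiting are the only postoperative harms recorded, so the intrathecal morphine arms can be weighed against Group P on only part of the opioid cost

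*Combined protocol and SAP*

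**What the plan says.** The Study Protocol section sets the aim as a comparison of the combination with each component alone on morphine consumption, pain and recovery quality over 48 hours. It plans 90 adults aged 18 to 90, ASA I-IV, 30 per group. No safety outcome is part of the aim.

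Under Groups, the text for both Group M and Group P+M reads "Subarachnoid block will be administered at the L3-L4 intervertebral level by adding 10-15 mg bupivacaine with 100 µg of morphine". Group P has bupivacaine alone in the spinal. The later text of that section gives every group PCA morphine, and tramadol as rescue: "Rescue analgesia will be provided with 50 mg tramadol upon request" or at a VAS threshold.

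On harms, the same section says "Postoperative nausea and vomiting will be monitored and recorded", without a grading or time points. It also says that "all patients will be continuously monitored for signs of local anesthetic toxicity every 5 minutes", for 30 minutes, and that "patients who are hemodynamically and respiratory stable in the recovery unit will be transferred to the ward". The other listed data are VAS at 1, 6, 12, 24 and 48 hours, QoR-15 and the need for rescue analgesia.

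The Statistical Analysis section plans Pearson chi-square or Fisher-Freeman-Halton tests for occurrence rates, with Bonferroni correction for the detailed group comparisons. It does not say which occurrences.

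**The concern.** Intrathecal morphine is one of the two randomised components. It would be expected to lower later morphine use and pain, which are the measures on which the arms are compared. The opioid effects that could offset such a gain include respiratory depression, sedation, itching and urinary retention as well as nausea and vomiting. Of these, only nausea and vomiting are to be recorded.

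Suppose the trial finds M or P+M better than P on morphine consumption or pain. The report could then show the gain in full and the opioid cost in part, in a population that runs to age 90 and ASA IV. The plan has no provision for recovering the missing items afterwards. Abstraction from ward charts might be possible, but it would not be standardised across arms.

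**Working it through.** **What the plan collects.** The plan states no event rate, power or effect size, so there is no figure of its own to reproduce. The first check is a reading of each safety-related statement against the 48-hour period.

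| Statement (section) | Recorded as data? | Covers the 48 hours after surgery? |
|---|---|---|
| Nausea and vomiting (Groups) | Yes | Postoperative; times not given |
| Local anesthetic toxicity checks (Groups) | Not stated | No; 30 minutes after the block |
| Stability before ward transfer (Groups) | Not stated; a condition for transfer | No |
| SpO2, EKG, blood pressure (Study Protocol) | Not stated | No; operating-room monitoring |
| QoR-15 (Study Protocol, Groups) | Yes | A global recovery score; gives no count of any single harm |
| Tests of occurrence rates (Statistical Analysis) | Variables not named | A test creates no data |

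Only the first row yields counts of a postoperative harm by arm.

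**Which contrasts are affected.** PCA morphine is available in all three arms and tramadol is rescue in all three. The randomised opioid difference is therefore the intrathecal dose: present in M and P+M, absent in P. It separates M from P and P+M from P, but not P+M from M.

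**What the extra data could show.** Inputs: n = 30 per arm (Study Protocol); significance level 0.05 (Statistical Analysis), taken as two-sided; Bonferroni for three pairs, 0.05/3 = 0.0167. Assumed harm rates: 30-50% with intrathecal morphine and 5-10% without.

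Exact power is the sum, over all pairs (x, y) for which Fisher's two-sided p is at or below the significance level, of Bin(x; 30, p1) × Bin(y; 30, p2).

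| Assumed rates | Power at 0.05 | Power at 0.05/3 |
|---|---|---|
| 30% v 10% | 37% | 22% |
| 30% v 5% | 63% | 47% |
| 40% v 10% | 71% | 54% |
| 40% v 5% | 89% | 79% |
| 50% v 10% | 91% | 82% |
| 50% v 5% | 98% | 95% |

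So common harms that differ widely between arms would probably be detected, and smaller differences would often be missed.

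**Rare harms.** With 0 events in n patients, the upper limit of the exact two-sided 95% interval is 1 − 0.025^(1/n).

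- One arm: 1 − 0.025^(1/30) = 11.6%.
- Both intrathecal morphine arms pooled: 1 − 0.025^(1/60) = 6.0%.

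The chance of seeing at least one event in 30 patients is 1 − (1 − p)^30. This is 26% at p = 1%, 45% at 2% and 79% at 5%. For uncommon harms the data could describe and bound, and no more.

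**The case against.** The strongest reply is that the plan does address cost. Nausea and vomiting are an opioid harm and are recorded. QoR-15 is a patient-rated recovery score and a stated outcome, so part of the burden of side effects may register there. This stands: the gap covers part of the cost, not all of it. A reader might infer that the trial can show a benefit and nothing of its price, and the documents do not support that.

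A reader might also infer that the design favours the morphine arms. It does not. Leaving a harm unrecorded does not shift the estimates of morphine use, pain or QoR-15, and the plan announces no safety claim. What is limited is the benefit-risk reading of the morphine arms against Group P.

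Two further points stand. Group P may use more PCA morphine, so the net difference in opioid harms between arms is uncertain, and the assumed rates have no support in the documents. And 30 per arm can neither compare nor exclude a rare serious event such as respiratory depression, so the value of the extra data is mainly descriptive.

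None of this supplies the missing counts. The toxicity checks, the transfer condition and the unnamed variables in the Statistical Analysis section do not collect them.

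**Conclusion.** The point holds as a gap in data collection. Nausea and vomiting are the only postoperative harms that the plan records, while intrathecal morphine is randomised to two of three arms. Comparisons of M and P+M with P can therefore be weighed against only part of the opioid cost. The efficacy comparisons stay valid, and the gap matters least for P+M versus M.

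The value of closing it depends on how common the harms are. Under the assumed 30-50% v 5-10%, pairwise power at 30 v 30 runs from 37% to 98% unadjusted and from 22% to 95% at 0.05/3. For an event not seen at all, an arm of 30 leaves rates up to 11.6% open. The extra data would support estimation with intervals, not a finding that either technique is safe.

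The conclusion assumes that no harm list stands in the front pages, which were not available for this review.

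**What to change.** At the 1, 6, 12, 24 and 48-hour assessments already planned for VAS, have the assessors already planned also record four items, each defined in advance:

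- respiratory rate;
- a sedation score;
- itching (yes/no);
- urinary retention or catheterisation (yes/no).

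Name these, with nausea and vomiting, in the Statistical Analysis section. Report counts by arm with exact two-sided 95% intervals beside the efficacy results (for respiratory rate and sedation, counts beyond a cut-off set in advance). State that the table is descriptive, and that zero events in 30 is compatible with a rate of up to 11.6%.

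The cost is four fields on the form, a little data entry and one table. No change to patient care is implied.
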